7.1.6. Local Site Injection Tolerability Assessment (SC Only)

Assessments made of the injection sites in the abdominal fat fold to monitor local tolerability to PF-06801591 SC injections will be performed for at least 1 hour following study drug administration, as per the [Schedule Of Activities](#). If SC injections in the abdominal location are not possible, SC injections can be administered in a distributed manner in the thighs. SC injections in the upper extremities (eg, deltoid, upper and lower arm) are not permitted. Refer to [Appendix 9](#) for more details.

Site tolerability assessments should continue after each dosing day visit, only if injection site pain or injection site reaction (ISR) characteristics continue to persist. The assessments should continue at regularly scheduled visits until the symptoms resolve. The injection sites will be assessed for erythema, induration, ecchymosis, injection site pain, injection site pruritus, or other observed characteristics after study drug dosing. The diameter of the affected area will be measured and the condition of the injection site will be recorded on the SC Injection Site Assessment CRF. Any observed abnormality at the injection site will be judged by the investigator to determine whether a corresponding AE should be reported. ISRs should be immediately photographed in color, with scaled ruler placed by the reaction, and these photographs should be included in the patient's source documentation. When appropriate, at the discretion of the investigator, a patient with an ISR may be referred for a dermatological consultation and skin biopsy may be obtained for future examination of the ISR. The dermatology consultation is expected to take place at the dermatologist's practice location, or may occur within the same institution where this study is conducted.

7.2. Pharmacokinetic Assessments

7.2.1. Blood for PK analysis of PF-06801591

Blood samples (approximate 5 mL) to provide serum for the analysis of PF-06801591 concentrations will be collected as outlined in the [Schedule Of Activities](#). The PK sampling schedule may be modified based on emerging PK data.

In addition to samples collected at the scheduled times, an additional blood sample should be collected from patients experiencing unexpected and/or serious AE's and the date and time of blood sample collection and of last dosing prior to PK collection documented in the CRF.

All efforts will be made to obtain PK samples at the scheduled nominal time relative to dosing. However, samples obtained within the protocol-specified time window will not be captured as a protocol deviation, as long as the exact time of the sample collection is noted on the source document and data collection tool (eg, CRF). If a scheduled blood sample collection cannot be completed for any reason, the missed sample time may be re-scheduled with agreement of the clinical investigator, patient, and sponsor.

Sample for PK analysis will be assayed for PF-06801591 using a validated analytical method in compliance with Pfizer standard operating procedures. To increase the understanding of the PK of PF-06801591, samples may be used for the evaluation of the bioanalytical method **CCI**. These data will not be included in the clinical study report. Details regarding the collection, processing, storage, and shipping of the blood samples will be provided in the study manual.

7.3. Biomarker and Pharmacodynamic Assessments

Biopsies and tissue samples (including but not limited to tumor, peripheral blood, and plasma) will be collected before and after PF-06801591 dosing for biomarker evaluation and pharmacodynamic assessments.

Archived Biopsy Samples

All patients are required to provide an archival tissue sample at screening, or agree to a de novo tissue sample collection per institutional procedural standards. In Part 2, Patients must provide FFPE tissue from the most recent primary or metastatic tumor biopsy or resection prior to study entry, taken within 2 years of start of study treatment.

Fresh Biopsy Samples

Fresh tumor biopsies are optional (within 28 days of first dose) for the first 2 to 4 patients in Part 1A at each dose level and in Part 2 if adequate archival tissue is provided at baseline, but fresh biopsies are mandatory in Part 1B at screening (within 28 days of first study treatment dose) and on-treatment (on Cycle 2 Day 8 \pm 5 days). Optional biopsies are encouraged at disease progression and/or end of treatment (assuming available tumor to biopsy) and as clinically indicated throughout treatment for all patients. If biopsy is to be completed the same day as CT scan, it must be completed after the CT scan.

Blood and plasma will be collected at the time points specified in the [Schedule Of Activities](#).

CCI [REDACTED] PD-1 RO on T-cell subsets will be evaluated in whole blood by flow cytometry in Part 1 only.

CCI [REDACTED]

The primary objective of these analyses will be to confirm target occupancy, CCI [REDACTED]

Table 5 summarizes representative assays to be used and the source of the samples. Refer to the [SCHEDULE OF ACTIVITIES](#) for details pertaining to specific days of sample collection and to the Lab Manual for details of sample preparation, storage, and shipment.

Table 5. Sampling and Assays for Biomarkers

Biomarker	Matrix	Assay
PD-1 Receptor Occupancy (Part 1 Only)	Whole Blood	Flow Cytometry

CCI

7.4. Tumor Response Assessments

Tumor assessments will include all known or suspected disease sites. Radiographic assessments obtained per the patient's standard of care prior to enrollment into the study do not need to be repeated and are acceptable to be used as baseline evaluation, if, (1) obtained within 28 days before C1D1, (2) performed using the method requirements (ie, RECIST v. 1.1), (3) the same technique/modality can be used to follow identified lesions throughout the trial for a given patient, and (4) appropriate documentation indicating that these radiographic tumor assessments were performed as standard of care is available in the patient's source notes. Radiographic images may potentially be collected for central review.

Acceptable imaging may include CT, MRI (with contrast at minimum) of the chest, abdomen and pelvis, or other radiographic disease sites as clinically indicated. Brain MRI or CT scans will be performed at baseline and on-study for patients with known or suspected brain metastases or if disease is suspected or has been previously documented as appropriate to follow disease. Baseline central nervous system (CNS) imaging is not required with the exception of symptomatic patients to rule out CNS metastases. FDG-PET may be performed for further characterization of tumors, but any CT scans performed concurrently with PET must be of diagnostic quality with contrast in order to be used for tumor assessments. Bone scans should be performed at baseline and on-study for patients with known or suspected bone metastases not well-visualized on other imaging or if disease is suspected or has been previously documented as appropriate to follow disease.

The same imaging technique used to characterize each identified and reported lesion at baseline will be employed in the following tumor assessments whenever possible.

Anti-tumor activity will be assessed through radiological tumor assessments conducted at baseline, during treatment as specified in the [Schedule Of Activities](#), whenever disease progression is suspected (eg, symptomatic deterioration), and at the time of withdrawal from treatment, if not done in the previous 3 weeks, after end of treatment for patients who did not end treatment due to disease progression, death, or withdrawal of consent, a tumor assessment will be performed every 12 weeks until disease progression by irRECIST, initiation of a new anti-cancer treatment, or end of trial (2 years after LPFD, see [Section 13.2](#)), whichever is first. Note: If a patient is classified as having PD during an on-treatment tumor assessment, then confirmation of PD by a second scan in the absence of rapid clinical deterioration is required per irRECIST.

CT or MRI scans to be done every 6 weeks (± 5 days) for patients on IV administration portion and every 8 weeks (± 5 days) for Parts 1 and 2 SC administration portion from the start of study entry (defined as C1D1) until disease progression by immune-related RECIST (irRECIST), death, withdraw consent, or subsequent administration of an anti-chemotherapy agent. CT or MRI scans may be assessed every 12 weeks (± 5 days) for patients who 1) have remained on treatment for ≥ 24 weeks, and 2) have no confirmed progression by irRECIST within the last 6 months, and 3) have demonstrated stability of disease. Tumor assessments should be fixed according to the calendar, regardless of treatment delays.

Confirmation of response (complete response [CR]/partial response [PR]) with a second consecutive scan at least 4 weeks later is preferred. Tumor assessments should be repeated at the End of Treatment visit if more than 6 weeks (IV) or 8 weeks (SC) have passed since the last evaluation. CT or MRI scans should be completed before tumor biopsy samples are collected. If a patient is classified as having progressive disease (PD) at a post-baseline tumor assessment, then confirmation of PD by a second consecutive scan at least 4 weeks later in the absence of rapid clinical deterioration is required. After End of Treatment for patients who did not end treatment due to disease progression, death, or withdrawal of consent, a tumor assessment will be performed every 12 weeks (± 1 week), until disease progression by irRECIST, or initiation of a new anti-cancer treatment, or end of trial (2 years after LPFD, see [Section 13.2](#)), whichever is first.

If imaging is used in disease assessment, the same imaging technique used to characterize each identified and reported lesion at baseline will be employed in post-baseline disease assessments whenever possible.

Disease response assessments will be based upon disease-specific response criteria: RECIST v 1.1 ([Appendix 3](#)) and irRECIST ([Appendix 4](#)).

7.5. CA-125 Tumor Marker Assessment (Ovarian Cancer Only)

Serum CA-125 is the standard for tumor markers in the evaluation of pelvic masses, particularly epithelial ovarian cancers. During treatment for ovarian cancer, CA-125 is a helpful indicator of disease activity and can be used to follow response to therapy and detect an early recurrence.^{55,56} The first measurement for CA-125 must be collected within 2 weeks before treatment is started, during the screening period. Subsequent CA-125 levels will be measured on Day 1 of each cycle before treatment, at End of Treatment, and at Follow-up

visit 28 days after last dose administration. There is no need to repeat on C1D1, if the baseline (screening) assessment was performed within 72 hours prior to that day.

7.6. Immunogenicity Evaluations

Blood samples (approximately 10 mL) to provide serum for detection of anti-drug antibody (ADA) and neutralizing antibodies (Nab) against PF-06801591 will be collected into appropriately labeled tubes at times specified in the [Schedule Of Activities](#). Additional instructions for sample collection, processing, storage, and shipping will be provided in the lab manual. A companion blood sample for the determination of PF-06801591 concentration will be collected in conjunction with the ADA sample collection to facilitate immunogenicity assessment.

The ADA samples will be analyzed using a validated assay in compliance with Pfizer standard operating procedures. The sample analysis will follow a tiered approach of screening, confirmation, and titer determination. Samples tested positive for ADA will be further analyzed for NAb using a validated assay in compliance with Pfizer standard operating procedures.

As part of understanding the immunogenicity of the study drug, samples may be used for additional characterization of an observed immunogenicity response and/or evaluation of the bioanalytical method. These data will be used for internal exploratory purposes and will not be included in the clinical report. Samples collected for this purpose will be retained in accordance to local regulations and, if not used within this timeframe, will be destroyed.

CCI

CCI

CCI

CCI

8. ADVERSE EVENT REPORTING

8.1. Adverse Events

All observed or volunteered AEs regardless of treatment group or suspected causal relationship to the investigational product will be reported as described in the following sections.

For all AEs, the investigator must pursue and obtain information adequate both to determine the outcome of the AE and to assess whether it meets the criteria for classification as an SAE requiring immediate notification to Pfizer or its designated representative. For all AEs, sufficient information should be obtained by the investigator to determine the causality of the AE. The investigator is required to assess causality. For adverse events that the investigator deems immune-related, that specific causality and whether an immunosuppressive therapy (eg, corticosteroids, other immunosuppressant drugs) is indicated, will be recorded on the CRF. For any adverse event, regardless of investigator determined causality, if the management requires administration of an immunosuppressive therapy, the use will be documented on a specific case report form that will record generic drug name, stop and start dates (duration), dose, units, route, frequency of administration, and response to medication. Follow-up by the investigator may be required until the event or its sequelae resolve or stabilize at a level acceptable to the investigator, and Pfizer concurs with that assessment.

As part of ongoing safety reviews conducted by the sponsor, any non-serious AE that is determined by the sponsor to be serious will be reported by the sponsor as an SAE. To assist in the determination of case seriousness, further information may be requested from the investigator to provide clarity and understanding of the event in the context of the clinical study.

8.2. Reporting Period

For SAEs, the active reporting period to Pfizer or its designated representative begins from the time that the patient provides informed consent, which is obtained prior to the patient's participation in the study, ie, prior to undergoing any study-related procedure and/or receiving investigational product, through and including 150 calendar days after the last administration of the investigational product or until administration of subsequent anti-cancer therapy whichever comes first. Death must be reported as an SAE if it occurs within 150 calendar days after last administration of the investigational product, irrespective of any intervening treatment. SAEs occurring to a patient after the active reporting period has ended should be reported to the sponsor if the investigator becomes aware of them. At a minimum, all SAEs that the investigator believes have at least a reasonable possibility of being related to investigational product are to be reported to the sponsor.

If an SAE occurs after informed consent is signed and before study drug is administered, this information will be reported on an SAE Form and will be recorded in the safety database.

AEs (serious and non-serious) should be recorded on the CRF from the time the patient has taken at least 1 dose of investigational product through the patient's last visit. Patients must be followed for AEs for 28 days after the last treatment administration or until all drug related toxicities have resolved, whichever is later; or earlier than 28 days should the patient commence another anticancer therapy in the meantime. Additional, immune-related AEs will be collected with a follow-up phone call at 90 and 120 days after last dose administration date to collect post-treatment related AE information.

If a patient begins a new anticancer therapy, the AE reporting period for non-serious AEs ends at the time the new treatment is started.

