Any additional treatment beyond 2 years shall be discussed and approved by the sponsor. Patients will be allowed to stay on treatment in the case of initial radiological disease progression, if the investigator feels that it is in the patient's best interest. For example, if a patient does not have rapid clinical deterioration, after initial assessment demonstrating unconfirmed PD. If a patient has a confirmed CR (ie, 2 consecutive CR assessments at least 4 weeks apart) by irRECIST, patient may also discontinue treatment at the discretion of the investigator and continue follow-up assessments.

3. Will complete a 1 month follow-up visit after the last dose for adverse event (AE) collection and serious adverse event (SAE) follow-up if necessary.
4. Will undergo assessment for late immune related AEs (irAEs) up to 120 days after completion of PF-06801591 administration(see [Section 3.1.5.1 Late Immune-Related Dose-Limiting Toxicities](#)). Subsequent anti-cancer therapy will also be recorded during these follow up visits.
5. Will be contacted by telephone every 8 weeks for survival data collection after the 120-day follow-up visit, until the end of the trial (defined as 2 years after last patient first dose [LPFD], see [Section 13.2](#)). Subsequent anti-cancer therapy will also be documented during survival follow-up visits.

Study Objectives and Endpoints

Part 1 Dose Escalation

Primary Objective(s):	Primary Endpoint(s):

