- v. **AE Assessments:** Adverse events should be documented and recorded at each visit using NCI CTCAE version 4.03. AEs (serious and non-serious) should be recorded on the CRF from the time the patient has taken at least 1 dose of investigational product. Patients must be followed for AEs for 28 days after the last treatment administration or until all drug related toxicities have resolved, whichever is later; or earlier than 28 days should the patient commence another anticancer therapy in the meantime. Additional, irAEs will be collected with a follow up phone call at 90 and 120 days after last dose administration date to collect post treatment related AE information.
- w. **SAE Assessments:** For SAEs, the active reporting period to Pfizer or its designated representative begins from the time that the patient provides informed consent, which is obtained prior to the patient's participation in the study, ie, prior to undergoing any study related procedure and/or receiving investigational product, through and including 150 calendar days after the last administration of the investigational product or until administration of subsequent anti-cancer therapy whichever comes first. SAEs occurring to a patient after the active reporting period has ended should be reported to the sponsor if the investigator becomes aware of them; at a minimum, all SAEs that the investigator believes have at least a reasonable possibility of being related to investigational product are to be reported to the sponsor.
- x. **Concomitant Medications and Non Drug Supportive Interventions:** all concomitant medications should be recorded in the CRF including supportive care drugs (eg, Anti-emetic treatment and prophylaxis), drugs used to treat adverse events or chronic diseases, and non-drug supportive interventions (eg, transfusions).
- y. **Subsequent anticancer therapy:** After the completion of the EOT visit subsequent anti-cancer therapy will be documented and recorded for patients who discontinue investigational products and continue in 120 day safety follow-up, and subsequently during survival follow-up.

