- z. **Contraceptive Check (frequency to match that of pregnancy tests):** Male patients who are able to father children and female patients who are of childbearing potential will need to affirm that they meet the criteria for correct use of 2 of the selected methods of contraception throughout the study and continue for at least 5 months after the last dose. The investigator or his or her designee will discuss with the patient the need to use 2 highly effective contraception methods consistently and correctly and document such conversation in the patient's chart. In addition, the investigator or his or her designee will instruct the patient to call immediately if one or both selected contraception methods are discontinued, or if pregnancy is known or suspected in the patient or the patient's partner.
- aa. **Subsequent Cycles:** For Blood PK samples for PF-06801591 and for PD-1 Receptor Occupancy samples (whole blood) refer to the separate PK & Pharmacodynamic [Schedule of Activities](#).
- bb. **End-of-Treatment Visit:** conducted at the visit that the patient is discontinued from the trial and no longer than 1 week after the patient has been discontinued. Complete tumor assessments if not completed in the last 8 weeks.
- cc. **1-Month and Late irAE Follow-up:** At least 28 days and no more than 35 days after discontinuation of treatment or last dose of study drug whichever is later, patients will return to undergo review of concomitant medications, vital signs, and assessment for resolution of any treatment-related toxicity. Patients continuing to experience toxicity at this point following discontinuation of treatment will continue to be followed at least every 4 weeks until resolution or determination, in the clinical judgment of the Investigator, that no further improvement is expected. To collect additional late immune-related AE information, all patients will have a follow-up phone call 90 and 120 days (± 7 days) after last dose administration date to collect post-treatment related AE information. If any concern arises, the patient will be called in for an inpatient

follow-up visit within 5 calendar days of the initial phone call (assessments will be the same as the assessments performed 28 days (range 28-35 days) after EOT follow-up visit).

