6.4. Follow-up for Late Immune-related Adverse Events

Patients will undergo telephone follow-ups at 90 and 120 day (± 7 days) after the last dose of study drug to assess potential late irAEs. If any concern arises, patient will be called in for an inpatient follow up visit within 5 calendar days of initial phone call. For this inpatient follow-up visit, the [Schedule Of Activities](#) will be similar to the 1-month follow-up visit completed after EOT.

Patients continuing to experience late immune-related toxicity at this point (up to 120 days after last dose of study drug) will continue to be followed at least every 4 weeks until resolution or determination, in the clinical judgment of the investigator, that no further improvement is expected.

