6.6. Patient Withdrawal

The reason for a patient's discontinuation from treatment will be documented in the end of study/withdrawal CRF. Patients will be followed for at least 120 days after the last dose of study drug for AEs.

Patients may withdraw from treatment at any time at their own request, or they may be withdrawn at the discretion of the investigator or sponsor for safety or behavioral reasons, or the inability of the patient to comply with the protocol-required schedule of study visits or procedures at a given study site.

Reasons for withdrawal of study treatment may include:

- Objective disease progression;*
- Global deterioration of health status requiring discontinuation;
- Unacceptable toxicity;
- Pregnancy;
- Significant protocol violation;
- Lost to follow-up;
- Patient refused further treatment;
- Study terminated by sponsor;
- Death.

*In the case of radiological progression but in the absence of clinical deterioration, if investigator deems it to be in the patient's best interests, the patient will be allowed to stay on study.

Reasons for withdrawal from study follow-up may include:

- Completed study follow-up;
- Study terminated by sponsor;
- Lost to follow-up;
- Refused further follow-up;
- Death.

If a patient does not return for a scheduled visit, every effort should be made to contact the patient. All attempts to contact the patient and information received during contact attempts must be documented in the patient's medical record. In any circumstance, every effort should be made to document patient outcome, if possible. The investigator should enquire about the reason for withdrawal, request the patient to return for a final visit, if applicable, and follow-up with the patient regarding any unresolved AEs.

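### Safety tables close at last dose + 28 days or new anticancer therapy, so late immune-related AEs sought at the day 90 and 120 calls reach listings only; Protocol 8.2 also leaves their collection after a switch unclear

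*Protocol*

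**What the plan says.** **Analysis.** SAP 6.2.2 (Safety Endpoints, Part 1 and Part 2) admits to tables only on-treatment data, from first dose to the earlier of last dose plus 28 days and the start of other anticancer therapy. Listings hold everything collected. DLTs are summarized separately under SAP 6.2.1, for Part 1 only. AE frequency, severity and timing are primary endpoints in both Parts (Protocol 2.1 and 2.2, SAP 3.1).

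**Collection.** Protocol 8.2 says: "Additional, immune-related AEs will be collected with a follow-up phone call at 90 and 120 days after last dose administration date". Its closing sentence then reads: "If a patient begins a new anticancer therapy, the AE reporting period for non-serious AEs ends at the time the new treatment is started". No sentence in 8.2 names irAEs as exempt from that stop or subject to it. For serious events, 8.2 keeps reportable at least "all SAEs that the investigator believes have at least a reasonable possibility of being related to investigational product", and deaths within 150 days whatever treatment intervenes.

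Other places set no stop at new therapy:
- Section 6.4 has telephone contacts at days 90 and 120 "after the last dose of study drug to assess potential late irAEs".
- Section 6.6: "Patients will be followed for at least 120 days after the last dose of study drug for AEs".
- The Schedule follow-up footnotes (ee for Part 1 IV, ff for Part 1 SC, cc for Part 2): "all patients will have a follow-up phone call 90 and 120 days".
- In the Schedule AE footnotes (x, y and v respectively), new therapy shortens only the basic 28-day follow-up, "or earlier than 28 days should the patient commence another anticancer therapy in the meantime". The irAE calls follow without a limit.
- The Protocol Summary, on the late-irAE contacts: "Subsequent anti-cancer therapy will also be recorded during these follow up visits".

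**The concern.** The late contacts exist because checkpoint-inhibitor toxicity can appear well after dosing stops. If the tables close before the first of these contacts, what the contacts find cannot enter a reported AE rate. A reader of the main AE tables would see irAE frequency through roughly one month after the last dose and could take it as the whole record. Part 2 has no DLT endpoint, so for its approximately 100 patients there is no second route into a summary table.

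The collection question lies upstream of this. A patient who stops PF-06801591 and starts another agent before day 120 is still called. If the closing sentence of 8.2 governs, a non-serious irAE that began after the switch need not be recorded, and then even the listing lacks it. If 6.4, 6.6 or the footnotes govern, it is recorded.

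**Working it through.** **1. What the tables can cover.** The inputs are the SAP 6.2.2 cut-off (last dose + 28 days at the latest), the protocol irAE follow-up (to day 120 after last dose) and the call window (±7 days).
- Largest share of the 120 days that can be tabulated: 28/120 = 23%. It is smaller if new therapy starts before day 28.
- Earliest in-window day-90 call: 90 − 7 = day 83.
- Gap from the latest table cut-off to that call: 83 − 28 = 55 days.
- Even the one-month visit, allowed at days 28 to 35, can fall up to 35 − 28 = 7 days past the cut-off.

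The calls can still add to the tables by picking up an irAE with onset before the cut-off. An irAE with later onset cannot be tabulated, whether serious or not.

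**2. Whether drug is still present at the cut-off.** Protocol 1.1 and 1.5 project a half-life of about 3 weeks. Then 28/21 = 1.33 half-lives have passed at day 28. Assuming simple first-order decline, about 0.5^1.33 = 40% of the concentration remains. Tabulation therefore stops while exposure is substantial.

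**3. Size of the understatement.** Let E be patients with a first irAE before the cut-off and L those whose first irAE comes after it and by day 120. The tables show E, the full record is E + L, and the shortfall is L/(E + L). The documents give neither L nor a switching rate, so no value follows. The 23% is a share of calendar time and says nothing direct about the share of events.

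**4. Collection after a switch.** Take a patient who starts new therapy on day X < 120 after last dose and has a non-serious irAE with onset between X and 120.
- 8.2, closing sentence: outside the reporting period.
- 8.2, the sentence on the calls: collected.
- 6.4: the calls take place; no stop at X.
- 6.6: AE follow-up continues to at least day 120; no stop at X.
- AE footnotes x, y and v: new therapy shortens the 28-day period only.
- Follow-up footnotes ee, ff and cc: calls for every patient.

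No passage ranks these. If the irAE is serious and possibly related, or is an important medical event reported as serious (8.6), it stays reportable, so this gap is confined to non-serious irAEs.

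**The case against.** **On the tables.** A window of 28 days or new therapy limits misattribution, and the listings hide nothing. SAP 6.2.2 also says its AE summaries span the entire study period, which a reader might take to include late events. The first argument supports keeping the main tables as they are. It does not support leaving the events of two dedicated contacts without any summary. The second does not succeed: the section opens by confining tabulations to on-treatment data, and the whole-period wording distinguishes those summaries from the by-cycle ones.

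**On 8.2.** The section can be read as one rule, with collection described first and then closed at a switch. It shows how an exception is written (deaths) and writes none for irAEs. Recording subsequent therapy at the calls may serve only to date the cut-off, and the calls keep other uses for switched patients, such as SAEs and irAEs that began earlier. This is a fair reading, so the text is ambiguous and not flatly contradictory. It still does not fit the 120-day follow-up in 6.6 or the footnotes, where the stop is absent.

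**Stronger inferences a reader might draw.** One is that the MTD or the chosen dose is at risk, because a late immune-related DLT could go unrecorded. The documents do not support this. The 300 mg SC dose was already selected for Part 2 (Protocol 3.1.2, 3.1.8), the SC portion has one planned level whose data do not inform IV escalation (3.1.4), and late-DLT observation has its own rule (3.1.5, 3.1.5.1). Another is that sites will in fact differ or that data will be lost; that is inference, with no switching rate to size it.

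**Conclusion.** The table exclusion follows directly from SAP 6.2.2 and holds however 8.2 is read: irAEs with onset after the cut-off have no frequency table unless they are summarized as DLTs. This assumes that the sponsor's safety reporting standard, cited in SAP 6.2.2 but not reproduced, adds no late-irAE table. The extent in time is clear (at most 28 of 120 days tabulated); the extent in events is unknown.

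The 8.2 point is secondary and narrow. It affects non-serious irAEs that begin after new therapy, under one of two tenable readings. It would be wrong to infer that serious late irAEs go uncollected: related SAEs, important medical events and deaths within 150 days remain reportable. Overall this is a cheap improvement of low to moderate priority that does not threaten the trial's conclusions.

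**What to change.** **SAP 6.2.2.** Keep the existing tables. Add a separate irAE summary from first dose through day 120 after last dose, split by onset before or after the start of new anticancer therapy. Use the immune-related causality already recorded on the CRF under Protocol 8.1.

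**Protocol 8.2 and Schedule AE footnotes x (Part 1 IV), y (Part 1 SC) and v (Part 2).** State that AEs deemed immune-related and at least possibly related to PF-06801591 are recorded through the day-120 call even if other anticancer therapy has started, and are flagged when onset follows that start. Leave the cut-off in force for other non-serious AEs. The relatedness condition, applied through the causality assessment in 8.9, avoids a duty to record irAEs attributed solely to a later immunotherapy. If the sponsor does want irAE collection to end at a switch, it should say so in 8.2, 6.4, 6.6 and the footnotes.

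**Cost.** One SAP table, one clause in 8.2 and three footnotes, and one flag derived from the therapy start date. No new visits or causality fields are needed. The downside is less certain attribution once another agent is on board; the flag and the split make that visible.
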